The Bangladesh Integrated Nutrition Project (BINP) of the Government of Bangladesh has started showing reduction in malnutrition of women and children under two years of age in last 3 years of it's activities. Moderately malnourished children form a large proportion of children in the community. With success of the BINP this proportion is farther increasing as severely malnourished children are improving and "graduating" to the moderately malnourished category. Recent operations research of BINP shows that it is possible to reduce moderate malnutrition substantially through a specific package of intensive nutrition education. (INE). That was a demonstration study to test the efficacy of the approach on a relatively small number of children with intensive intervention. There is now an urgent need to define an effective and feasible means applicable in a larger population in the country. A study will be therefore conducted in 4 division of BINP thanas of Bangladesh over an 18-month period. Moderately malnourished children will be in management intervention and mildly malnourished and well-nourished infants will be in preventive intervention group. For management intervention, a total of 750 moderately malnourished will be randomized to receive either intensive nutrition education or less intensive education. For preventive purpose, 380 mildly malnourished children of 6 months to 2 years of age and 100 well nourished infants of 6 to 9 months of age will receive either less intensive education or no education. Infants between 6 to 9 month ages will be brought under less INE to ensure their complementary feeding practice. Care givers of one group of mildly malnourished children and one group of 6-9 month old infants will not receive any education to serve as controls. Focus Group Discussion (FGD) based INE will be conducted taking into consideration of geographical variation for an in-depth understanding of culture. Focus group discussion will be held with mothers to discuss beliefs, food habits and feeding practices of these children. An anthropologist and a nutritionist will jointly develop the nutrition education package. INE on child caring and on food security and disease control. Mothers of the first intervention group will receive intensive nutrition education and motivation for childcare, complementary food demonstration, and household food mobilization for child feeding twice weekly for first three months, which will be then reinforced once in a week for the last three months of intervention. The less intensive intervention group will receive nutrition education with the same components twice a week for the first month then once a week for two months and then twice monthly for the last three months of intervention. INE will be given for a total of 6 months. An observation will be done to identify for sustainability effect for an additional period of 6 months. Their weight and length gain will be recorded. The Community Nutrition Promoter (CNP), Community Nutrition Organizer (CNO), women's group and village nutrition committee will be involved in motivating and

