
ensuring child caring practices. Data on morbidity will be collected and necessary medical advice for referral to the health centre will be given equally to each group. The CNP and CNO's time will be mapped and will be asked to adopt study messages to examine the practicality. Data collection, counseling on child caring practice, food demonstration and nutrition education using IEC will be organized and supervised by project staff. It is assumed that if the intervention is successful, and once the nutritional status improves, they are likely to maintain good health. The IEC on dietary practice will be communicated to the VNMC (village nutrition management committee) members for further preventive measures. Data on cost effectiveness of the nutrition education strategies will be collected by a health economist. Data will be analyzed for change in nutritional status from moderate to mild malnutrition or normal nutrition and proportions of children continuing complementary feeding will be compared between the intensive and less intensive intervention and control groups. It is expected that the results of the study will help define the effectiveness of our nutrition education package to prevent and reduce moderate malnutrition existing in large proportion of children in setting with different geographical, and cultural and feeding practices.

KEY PERSONNEL (List names of all investigators including PI and their respective specialties)

Name	Professional Discipline/ Specialty	Role in the Project
1. [name]	Scientist, ICDDR, B	Principal Investigator
2. [name]	Director, CSD, ICDDR,B	Co-Principal Investigator
3. [name]	Senior Medical officer ICDDR, B	Co-Investigator
4. [name]	BRAC, Bangladesh	Collaborative investigator

DESCRIPTION OF THE RESEARCH PROJECT

Hypothesis to be tested:

Concisely list in order, in the space provided the hypothesis to be tested and the Specific Aims of the proposed study. Provide the scientific basis of the hypothesis, critically examining the observations leading to the formulation of the hypothesis.

Hypothesis

- a. Less intensive nutrition education including food demonstration at the community level will be equally effective as intensive nutrition education for the prevention and reduction of moderate malnutrition.
- b. The effect of less intensive nutrition education given over a period of 6 months will sustain during the following six months without any intervention.

Specific Aims:

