FGD will be conducted on mothers in 6 groups each from 3 CNC's (1 control and 2 study areas). There will be 6-8 mothers of moderately malnourished children in each Focus Group Discussion. This is expected to be more or less homogenous, since mothers having young children in the villages are of similar age FGD will be conducted by the anthropologist. Moderator will play the role of guiding the group on the right topic by putting them on the track. The research personnel will facilitate discussion but they will not influence the discussion. A tape recorder will be used to record the discussion. One facilitator will take notes. Obtained data from FGD will be analyzed manually by using coding.

The FGD will be conducted again to evaluate the change in behaviour and the process indicators. The method indicated above will be followed in the later part of the study.

A pre-test on knowledge of child feeding practice will be done and will be repeated with same the questionnaire after the diet counselling sessions with the mothers. Data on feeding frequency, preparation of information on child feed, dietary ingredients, frequency of feeding and constraints will be recorded at two weekly intervals in study groups. Post test will be conducted at the end of

nutrition education period.

The health assistants will be pre-testing the nutrition knowledge of the mothers and mothers will be observed before actual training is given. These subjects will not be included into study. This will reduce observer bias of the health assistants.

Outcome variables:

1. Mothers understanding and ability to identify moderate malnutrition in children.
2. Mothers understanding on consequence of moderate malnutrition.
3. Change in knowledge of mothers in feeding practices.
4. Frequency of home feeding (Breast-feeding and supplementary feeding).
5. Frequency of seeking medical care during illness, referral, incidence, duration of illness.
6. Adequacy of child feeding, frequency & type of feeding.
7. Weight gain, weight for age and weight for height at the end of intervention.
8. Proportion of complementary feeds in 6-9 months age group.
9. Nutritional status of children at various phases of intervention and observation.
10. Adaptation level of nutrition education program by CNP, CNO.
11. Constant of not practicing education knowledge.

Secondary outcome variables: -

1. Incidence and prevalence of diarrhoea and ALRI
2. Referral success and failure
3. Resistance to education

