Data will be double entered in a microcomputer within a week of data collection. The field supervisors will visually check data before sending for entry into the computer. Any error, discrepancy or omission found during data entry will be reported to the investigators without delay. Data will be entered into microcomputer using SPSS Windows's program. Data on weight gain, frequency and introduction of complementary feeding will be compared between experimental groups. Complementary feed introduction and regularity will be compared among 6-9 month age groups in education and control groups. Comparability between intervention and control groups will be assessed by baseline characteristics such as age sex, nutritional status, socioeconomic characters, feeding practices, etc. Continuous variables will be assessed for normal distribution. T test will be performed to compare data of normal distribution; otherwise non-parametric test will be used. Chi-squared test will be performed for categorical variables, Multiple regression analysis will be done with weight gain as dependent variable and intervention and potential confounding variables such as age, sex, SES, baseline nutritional status, infection as independent variables. Separate analysis will be performed for periods of intervention, reinforcement and observation.

Compliance of nutrition education will be measured at 2 weekly observation period (already mentioned). Compliance will be measured as process indicator. Comparison of compliance will only

be done at the end of the study so that the investigators will have no idea about which group is more a less compliant. Therefore, these will be little change of introduction of bias due to non-compliance, effect of intensive or less intensive nutrition education will be compared as a whole. So complain will be seen as a factor of nutrition education with given intensive. Analysis of compliance data will be done by relating to the outcome effect of nutritional status and can be compared between two education groups.

Analysis of qualitative data

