For preparation of food and taking care of the child, mothers' time was critically important e.g. during harvesting period, mothers could find little time for cooking supplementary food as well as make the child feed by herself. Mothers cooked extra khichuri for children on 3-4 days a week. Alternate food mixes taught by health assistants were given from family pots during the weekdays. Many of the poor families could manage only one meal a day and could not afford to buy varieties and ideal ingredients to prepare complementary food. With frequent nutrition education, parents purchased dietary items which mothers

initially resisted because they perceived not essential for better child growth. Mothers reported that with the improvement in nutritional status of moderately malnourished children, their husband took more initiative to buy more special foods for their children. These items included soybean oil (usually cooking was done with mustard oil), eggs, lentils/dhal and different colored vegetables. Superstitions and food taboos on some food items were almost removed in the intervention groups.

Some improvements were also observed in the control group, which attributed to all or some of the following reasons: a) Two weekly nutrition education was given to mothers of the moderately malnourished children by CNPs and CNOs of the implementing NGO. b) The NGO workers (CNO/CNP) adopted and used specific messages from instruction of our health assistants at the field level. C) The baseline data on prevalence of malnutrition was collected immediately after the flood and therefore there was natural recovery in the first month in all the study groups after flood period. D) The study period covered the harvesting season enabling a better food intake in all groups.

Children from all groups were followed up for an additional period of 3 months after the intervention. The improvement weight gain continued steadily only in the intervention groups.

We concluded that, the substantial reduction in moderately malnourished children through nutrition education and SF has significant potential to reduce this staggering problem. Further research is needed to define the intensity of education needed to achieve sustained improvement.

[name], Hope this is helpful!

Reviewer - I

Best,
[name]

May 1999

TO: [name]

FROM: [name]

SUBJECT: Your O.R. Draft on Feasible Means to Address Moderately Malnourished Children

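### Hypothesis (b) needs a month-12 contrast of LINE with no education measured from entry; weight gain within the observation period, the natural reading of the plan, does not estimate the effect that remains

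*Protocol*

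**What the plan says.** Months below are counted from the start of education.

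- **Hypothesis.** Protocol, Hypothesis (b): "The effect of less intensive nutrition education given over a period of 6 months will sustain during the following six months without any intervention".
- **Follow-up.** Project Summary: "An observation will be done to identify for sustainability effect for an additional period of 6 months". The next sentence there says that weight and length gain will be recorded.
- **Analysis.** Data Analysis: "Multiple regression analysis will be done with weight gain as dependent variable". The covariates besides intervention are "age, sex, SES, baseline nutritional status, infection as independent variables", with no time point given for the baseline status. The next sentence is "Separate analysis will be performed for periods of intervention, reinforcement and observation".
- **Status outcomes.** Outcome variables, item 9: "Nutritional status of children at various phases of intervention and observation". Project Summary: "Data will be analyzed for change in nutritional status from moderate to mild malnutrition or normal nutrition". Neither is linked to hypothesis (b).
- **Groups.** Table 1 gives 375 moderately malnourished children to intensive education (INE), 375 to LINE and none to no education. The no-education groups are 190 mildly malnourished children and 50 well-nourished infants, set against equal LINE groups, with allocation by community nutrition centre (CNC). The replies to outside comments say that the mild children will not be compared with the moderate ones.
- **Measurement.** The design section schedules monthly weight and length for six months only.

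**The concern.** Hypothesis (b) is about a level: how much of the difference present at month 6 is still there at month 12. Gain within the observation period is an increment. The two behave differently. An effect kept in full gives a zero increment, and only an effect that is still growing gives a positive one. The investigators seem to think in increments: Annexure 4 supports persistence in the pilot by saying that the improved gain continued in the intervention groups.

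A second difficulty concerns the population. A LINE effect against no education needs a no-education group, and the moderately malnourished children have none. Their month-12 status under LINE also reflects age, season and recovery. Annexure 4 says of the pilot's post-flood baseline that "therefore there was natural recovery in the first month in all the study groups after flood period".

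The results are meant for immediate use by the national nutrition programme, so it matters that the statement on persistence rests on a contrast that can carry it.

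**Working it through.** The protocol gives no effect size, margin or sample size for hypothesis (b). Its two sample sizes rest on differences in proportions (15 points in moderate and 20 points in mild children). There is no stated figure to reproduce, so the check is algebra with an illustration.

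**1. Increment and level.** Let D6 and D12 be the group differences in mean weight gain from entry to months 6 and 12. The observation-period gain difference is G = D12 − D6. With D6 = d and D12 = r·d, G = (r − 1)·d.

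For d, take the pilot's three-month gap between education and control, 910 − 636 = 274 g. This is an assumption: it compares intensive education with standard advice in moderate children, not LINE with no education in mild children.

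| Course after month 6 | r | Difference from entry to month 12, r·d | Gain difference in observation period, (r − 1)·d |
|---|---|---|---|
| Grows by half | 1.5 | 411 g | +137 g |
| Fully kept | 1 | 274 g | 0 g |
| Half lost | 0.5 | 137 g | −137 g |
| All lost | 0 | 0 g | −274 g |

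**2. What an observed zero leaves open.** Take the 190 mild children per group, with the protocol's own 10% loss and design factor 1.5: 190 × 0.9 / 1.5 = 114 effective children per group. The standard error of a difference is SD × √(2/114) = 0.1325 × SD. The documents give no SD, so a range is assumed, and the same SD is used for both contrasts.

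| Assumed SD | 95% half-width, 1.96 × SE | As share of 274 g | Power for 274 g from entry to month 12 |
|---|---|---|---|
| 400 g | 104 g | 38% | 0.999 |
| 600 g | 156 g | 57% | 0.93 |
| 800 g | 208 g | 76% | 0.73 |

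An observation-period estimate of exactly zero would thus be compatible with losing between about a third and three quarters of the illustrative effect. The month-12 contrast from entry, if the effect is kept, would usually be detected.

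**3. Status outcomes.** For weight for age or the proportion moderately malnourished at month 12, a kept difference appears as a difference. The (r − 1) factor does not arise.

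**4. Moderate children.** Let L and I be the month-12 effects of LINE and INE against no education. The only between-group contrast available is L − I. If hypothesis (a) is true, L = I and the contrast is zero. It is zero when both effects are kept (274 − 274) and when both are gone (0 − 0). It cannot separate persistence from loss.

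**The case against.** **No restart is stated.** A reader might infer that the plan resets the baseline at month 6. It does not say so. The design section describes only an entry measurement as baseline, and the pilot's gains (436, 688 and 910 g) are cumulative from entry. This stands. Gain within each period is the natural reading, because the sentence follows the weight-gain model directly, but it is not the only one.

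**The sentence may cover more than gain.** It closes a paragraph that also plans chi-squared tests, and status is listed as an outcome during observation. A status comparison would not have this problem. That stands too, but nothing names such a comparison as the test of (b).

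**Zero is what persistence predicts.** A reader might conclude that a sustained benefit would be reported as a wrong answer. That goes too far. Loss would show as a negative difference, and the three period contrasts add up to the month 0 to 12 contrast if the same children are measured throughout. What remains is that no such sum is planned, and that failing to find a difference does not show that the effect was kept.

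**Randomisation is not lost.** A reader might say that later-period contrasts are no longer comparisons of the allocated groups. They are, as long as children stay in their groups. They answer a different question.

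**The missing no-education group is deliberate.** The ethical section says that all mothers of moderately malnourished children will receive education. Hypothesis (b) does not name moderate children, and the preventive groups do contain the needed contrast. The design therefore does not make (b) untestable.

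**Pilot controls are not an untreated course.** Their reduction in moderate malnutrition is given as 18% in the Background and 30% in Annexure 4. They received standard advice twice a month, and field workers took up study messages. Neither figure measures natural recovery.

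**Conclusion.** The point holds in limited form. On the natural reading, the analysis planned for the follow-up months estimates (r − 1)d and not the remaining effect r·d. It is never positive for an effect that is merely sustained, and a non-significant result near zero does not establish hypothesis (b). In the illustration the two quantities differ by the whole 274 g whatever r is. That size rests on the pilot gap, and the interval widths rest on assumed SDs of 400 to 800 g; the algebra rests on neither. Status outcomes that would avoid the problem exist, but the protocol does not assign them to (b).

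In moderate children, persistence of a LINE effect against no education cannot be estimated from any time point or baseline. This limits the claim and is not an error in the design. The documents do not support saying that the plan fixes a month-6 baseline or that it must give a wrong answer.

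Two inconsistencies add to the need for clear wording. Weight and length are scheduled for six months in one place, while recording during observation is implied in another. The replies to outside comments say that sustainability is not among the objectives, although it is hypothesis (b).

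**What to change.** For hypothesis (b), state that weight for age and nutritional-status category at month 12 will be compared between LINE and no education in the mildly malnourished children, as allocated by CNC, with the well-nourished infants as support. Measure from the pre-education baseline. Report the estimate with its confidence interval beside the same contrast at month 6, so that the size of the effect and the part retained are both visible.

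In moderate children, limit the month-12 statement to LINE versus INE. Keep gains within intervention, reinforcement and observation as descriptive results.

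Reconcile the six-month measurement schedule with the recording implied during observation, so that month-12 weight and length are secured in all groups. Align the reply on sustainability with hypothesis (b).

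The cost is analysis wording, provided that month-12 measurements are already intended; otherwise they must be added to the schedule. The downside is a narrower sustainability claim for moderately malnourished children.

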Sr. Field Res. Asstt.	GS-4 (12 months)		1	278	100%	3,336
Supervisors	GS-4 (CSA)		4	206	100%	14,832
Health Assistants	(CSA)		20	102	100%	36,720
Clerk	(CSA)		1	80	100%	1,440
Sub-total						105,090
2) Consultant :						
Collaborative Consultant ([name])				600	10%	1,080
Communication Specialist ([name])				600	20%	2,160
Sub-total						3,240
3) Travel:						
Local Projects						4,000
Dhaka and project site						3,500
International						4,500
Field visit honorarium						1,800
Sub-total						13,800
4) Supplies						
Office supplies						2,000
Medical supplies						1,000
Office furniture, cabinet etc.						2,000
Sub-total						5,000

5) Other Expenses :

Phone & fax	2,316
Printing and publication	1,440
Microcomputer & data analysis	3,000
Office rent	2,880
Dissemination seminars	2,000
Support for local community	2,000
IEC Materials	2,000
Sub-total	15,636

Total Direct Cost	142,766
Indirect Cost @ 15%	21,415

Total Project Cost US\$ \$ 164,181

[name]
Senior Budget & Cost Officer
ICDDR, B, [name].

Budget Justifications

Please provide one page statement justifying the budgeted amount for each major item. Justify use of man power, major equipment and laboratory services

PI: The principal Investigator will spent 25% of his time for the study and will be responsible for overall designs, monitoring of progress, quality control for whole research work and administration at every step.

Co-Principal Investigator: The co-principal investigator will help with design, decision making and actual planning of study (no funds).

Co-Investigators: Two ICDDR, B Co-investigators and one investigator for partner NGO, BRAC would be needed to make visits in 4 divisions and training of the senior level staff and their expertise would be as used in the project.

Senior Operation Researcher's: The Senior Operation Researcher will be necessary to assess the cost-effectiveness of the nutrition education strategies. He/She will mainly provide the guidance in designing the data collection instrument and analyzing the cost-effective data. His time will be needed for 18 months.

Communication Specialist: A Communication expert will help with training plan for health education and the strategy for implementation. Discussion structure would be developed for breast-feeding and other training issues. He will supervise strategies and IEC materials.

Nutritionist: A Nutritionist will be needed for developed lesson plans for the training of health assistants, training anthropometry, and other nutritional issues to the health assistants, intensive health education to the mothers, Visit food demonstration sessions and complementary feeding sessions, giving easy nutrition education to the mothers.

Anthropologist: An anthropologist will be needed to conduct Focus Group Discussions, conduct intensive training sessions for the health assistants, assuring quality of the data collected by the health assistants, and help with Nutritionist for FGD based health education training plan.

Senior Field Research Assistant: The Field Research Assistant will be assigned for collecting cost information, who will report to the Senior Operations Researcher of the Health Economics Programme, will be needed to supervise the field data collection and will be needed for full time for 12 months.

Supervisors: One in each division will supervise field work and maintain quality control for Health Assistants at field level for education, training and data collection.

Communication: Field visits from Dhaka to 4 divisions would be necessary to supervise monthly evaluation and progress of work at the field level. There will be transportation need; this will be for study area and for bringing staff and data to office and as necessary in community.

Dissemination: Dissemination will be done by seminar, productions of reports and publication in national and international nutrition and policy related journals. The results are expected to benefit developing countries in a unique and potential way. Which will be communicated through internal policy and program in the conferences.

Facilities: Analysis of data would require a microcomputer and other logistics would be required for running of the project.

Other Support

Describe sources, amount, duration, and grant number of all other research funding currently granted to PI or under consideration. (DO NOT EXCEED ONE PAGE FOR EACH INVESTIGATOR)

Time frame of the study

Months	1	2	3	4	5	6	7	8	9	10	12	13	14	15	16	17	18
Initial set up	■	■															
Staff training			■														
Operations Intense				■	■	■											
Operations Reinforce							■	■	■								
Observations										■	■	■	■	■	■		
Analysis																■	
Manuscript Writing																	■

Training plan:

In this study there will be three tiers of training sessions:

(A) A special core training session for project Nutritionist, Anthropologist, Medical Officer and field supervisors will conducted by Principal Investigator and co- Investigators.

Duration: 8 hours/day for 10 days.

Venue: ICDDR,B, Dhaka.

(B) A special core trainer session for health assistants will conducted by Medical Officer, Nutritionist, and Anthropologist.

Duration: 8 hours/day for 10 days

Venue: ICDDR,B, Dhaka.

(C) Training session¹ on the nutrition knowledge for the mothers':

Participants : Recruited subjects' mothers who will participate in FGD session.

Trainer : Health Assistants

Number of participants: Ten to twelve mothers in a group

Duration : Two hours

Sitting arrangement:

CNC areas with one or two mats for trainee mother /caretakers and a tool for trainer and a table for demonstration of complementary food preparation at the household level and discuss their new knowledge with each other.

Steps of the training session:

First steps: Current issue of social events.

Duration: Minimum 5 minutes.

Procedure: The trainer Health Assistants first introduces herself with all trainee mothers/caretakers and asks the participants to introduce themselves. Then the trainer will speak with all trainee mothers about current nutritional status for their children. Then the trainer will speak on about training issues.

Duration: 20 minutes.

Materials:

1. Colored IEC materials, Philip chart, posters on different nutrition items.

Topics: The trainer gives identified essential messages about breast feeding, weaning food items, complementary food preparation, child nutrition, caring practice, personal hygiene and sanitation according to the knowledge gap of the mothers/caretakers, found from FGD session.

[figure not shown]
j

About two hour later trainer will take feedback from the trainees about training session.

Participation in training sessions will be recorded.

¹ A bangla curriculum has been developed for the health assistants to the trainee mothers

Diagram reflection the communication strategy

Frequency and intensity of the two intervention groups

A. Intensive Nutrition Education

Topic	3 mon. Intervention (Frequency/week)	Number of training sessions	3 mon. Reinforcement: (Frequency/week)	Number of training sessions
Nutrition concept on diet	2 per week	24	1per week	12
CP, BF & Hygiene	1per week	12	1per 2week	6
Food Demonstration & House hold food mobilization	1per week	12	1per month	3
Referral/ Disease control	1per week	12	1per month	3

B. Less intensive Nutrition Education

Topic	3 mon. Intervention: (Frequency)	Number of training sessions	3mon. Reinforcement: (Frequency)	Number of training sessions
Nutrition concept on diet	2 per wk for 1 m.	8	1per week	4
	1per wk for next 2 m.	8	2 per month	4
CP, BF & Hyg	1per 2 week	6	1per month	3
Food Demonstration	1per 2week	6	1per month	3
HH Food mobilization	1per 2week	6	1per month	3
Referral/ Disease control	1per2week	6	1per month	3

Annexure-1

1: Nutrition and health education:

Malnutrition is not a medical and or a health problem alone. It is not a food scarcity and or a poverty problem either. It is rather a social problem stemmed out of ignorance, defective food habit, mistaken status identity, and related others. Addressing the issue of malnutrition thus demand interventions geared to behavior change which requires structured awareness building and educational efforts on nutrition and health.

1.a. Nutrition & Health Education Strategy.

A Nutrition & Health Education Strategy will be developed at the very beginning of the project based on the following considerations:

- that the project is an educational intervention;
- that less intensive education is to have greater focus over high intensive education to test its effectiveness for a nation-wide replication;
- that the audience (subject) will primarily cover illiterate/semiliterate women/families with some emphasis on local elite for their supportive and promotional roles;
- that the project is aim at sustainable behavioral change related to dietary practices, food preparation and consumption patterns and basic health care especially of your children, pregnant/lactating mothers and family members;
- that there will be set messages and tested food items for promotion;
- that there will be grassroots workers to reach the audience and their families; and
- that there be an in-built mechanism for monitoring of the effects leading to impact.

The Strategy will encompass the following specific activities :

- a. A review of existing information and knowledge regarding subject's (audiences') health and nutritional practices;
- b. Development of specific and alternative (to suit area/seasonal variations) messages related to different food items and its ingredients;
- c. Selection and training of health & nutrition workers on communication and motivational skills and on selected food items with their preparation based on set manual(s) and discussion guidelines;
- d. Appropriate supportive visual aids, samples/models will also be developed for interpersonal, organizational and community media;
- e. HNWs will then organize and conduct educational and motivational sessions with mothers, community members at individual and group levels;
- f. Localized advocacy efforts will also be initiated to mobilize support of local elite and community members; and
- g. Certain reminder materials like poster-calendars for families, booklets/leaflets for students and elite/leaders, flags for static centers, etc. will also be developed and used.

1.b. The Discussion Guidelines

Training of NHWs on Communication and Motivational Skills will be crucially important. These NHWs will eventually organize and conduct discussion sessions with mothers and others food items, its preparation and consumption. Accordingly, Manuals with lesson plans and discussion guidelines respectively will be developed to prepare and equip NHWs for the task.

The Discussion Guidelines for the NHWs to conduct the discussions with mothers will be based on the following steps :

- a. exploration of the subject's present practices with reasons;
- b. introduction of alternative practices and or food items as potentially better;
- c. presentation of economic, health and other benefits of the alternative(s);
- d. solicitation of subject's acceptance to test the alternative; and
- e. description and demonstration of its preparation and administration/
consumption.

This has to be followed by the subject's testing or trial to extend psychological support, responding to her/his additional queries and building faith and confidence in changing her/his behavior and practice.

A sample Discussion Guideline of shown below -

Session Title: Breast Feeding

Objectives : After the session, the participating mothers will be able to

- a. Identify Breast Milk as the best gift of nature/God to a mother and a child;
- b. Describe (some) the feeling while breast feeding their children;
- c. Explain the advantages and benefits of breast feeding;
- d. Describe the importance of colostrum and its administration; and
- e. Narrate the ideal breast feeding practices.

Duration : 120 minutes

Lesson Plan:

Objectives: Process	Content Points	Materials	Time
1. - Greet and welcome the participants			3m
- Introduce yourself and get others			7m
- Explain the objective and duration of the session	- Exchange experiences and new ideas on breast feeding	- Cards	2m
	- 90m		
- Share the importance of openness and participation	- Learning & help others to learn	- Illustration	5m

2. – Ask, what is the God’s/Natures’ best gift to a mother and a child ? - Probe and process the responses	- Views from participants - Mother’s milk	- Poster - Picture	5m 5m
3. - Ask, what are the present practices regarding breast feeding ?	- Views on colostrum, starting, frequency, duration, other foods, etc.	- Poster/ Picture	8m
4. – Synthesize and summarize		- Poster	5m
5. – Ask, what are your feelings while breast feeding your child ?	- Expressions of participants		10m
6. – Appreciate the expressions and note down the important points	- Important points	- Poster	5m
7. – Ask, what are the advantages and benefits of breast feeding ?	- Points from Participants	- Poster	10m
8. – Probe, process and present	- natures best gift and inexpensive - readily available in sufficient quantities - it is fresh and does not need worming - children love it and it bonds - it has preventive and anti-infective properties - it supplies essential nutrients ideal for child’s growth	- Poster	15m
9. – Add the following messages with explanation	- Colostrum must be fed to children as soon as child’s birth - Exclusive breast-feeding should be continued up to the age of six months. - Breast-feeding should be continued up to two years - Children should be fed with breast milk as many times as possible. - Learn about best practices about breast feeding for your and child’s benefit.	- Poster/Picture	15m
10. – Summarize the basic points to remember and thank everyone.			10m

Similar discussion structure will also be developed for other issues.

2. **Khichuri** will be explained and demonstrated how to prepare at home of a study subject.

Food ingredient	Quantity
Rice	2 fistful (65g)
Pulse	1 fistful (27g)
Oil	5 teaspoon full (30ml)
Potato	large (Hugh), small one piece (40g)
Sweet guard	small one piece (15g)
Green leafy vegetables	1 teaspoon after (15g)
	Cooking
	Egg/meat/fish 1piece (55g)
Water	4 glasses

Procedure:

900 k.cal (55g protein)

Required amount of rice, pulse and oil to be boiled in a container. After some times, potatoes are mixed and then sweet pumpkins to be added. Green leafy vegetables to be added 5 minutes after boiling of rice and to cover the container is to be covered for 25 minutes to cook the 'khichuri'.

After cooking the khichuri, its weight to be about 850 gram. Mothers' were advised to cook in her time preferably in the morning and feed. Khichuri in 5-6 schedules in a day.

The following procedure shown to prepare home made feeding for children:

3. Food cooked in the family are to be taken together such as cooked rice, dhal potato, vegetable fish or egg as available, thoroughly mixed and extra oil about 5-67 teaspoonful is added and feed to the child 4-5 times a day.
4. To show the mothers how to prepare a supplementary feeding packet at home, which was essentially the same as given in CNC by CNP. Roasted rice powder (40 g) roasted pulse powder (20 g) molasses (10g) and 6 g of oils about one teaspoonful. At the time of thoroughly mixing these ingredients, water has to be added to make consistency from thick to liquid according to the preference of child. Older child likes more thick and younger one likes more liquid.

About vegetables:

5. Vegetables are very important part of the diet. They are rich in β -carotene and vitamin C and contain significant amount of calcium, iron and other minerals.

6. Dark Green leafy vegetables (DGLV) are the most valuable because they contain more β -carotene and vitamin C, more calcium and iron, than pale green leaves and other vegetables.
7. Amaranth is much superior to cabbage or lettuce as it contains vitamins and mineral.
8. A green leafy and other vegetable play a major role in reducing vitamin A deficiency, and contribute to lessening the prevalence of iron deficiency anemia.
9. Dietary deficiency of vitamin A affects the eyes and it can lead to blindness.
10. The nutritive value of different seasonal fruits is their contents of vitamin C, B and energy.
11. Zinc is present in most foods of animal origin. Good sources include chicken, beef, mutton, sea fishes, legumes and wheat. Zinc deficiency has decreased efficiency of food utilization, poor growth, depressed gonadal functions, and frequent diarrhoea and other infection.

Iodine salt:

